# 1. Background and Rationale

Kidney transplantation is the preferred treatment for end-stage renal disease (ESRD) patients and is associated with increased quality of life and reduced mortality compared with dialysis. Nearly 17,000 kidney transplants are performed in the United States annually, and despite advances in improving early post-transplant outcomes, the need to improve long-term outcomes remains an important goal. Long-term immunosuppressive therapy is necessary to prevent rejection, but toxicity associated with immunosuppressive therapy can ultimately lead to decreased renal function and result in the need for re-transplantation. Traditional immunosuppressive regimens for kidney transplant consist of the calcineurin inhibitors (CNIs) cyclosporine A (CsA) and tacrolimus. These agents are associated with long-term renal toxicity and increase cardiovascular risk factors, including diabetes mellitus, hypertension, and hyperlipidemia.

The development of belatacept (trade name Nulojix), a member of a novel class of immunosuppressive medications known as selective T-cell costimulation blocking agents, represents a major advance in targeted immunosuppressive therapy. Immunosuppressive therapy with belatacept has been shown to improve renal function and has a favorable metabolic profile compared with CNIs. The mechanism of action of belatacept is more selective than that of previous immunosuppressants and its effect more specific; in animal models, belatacept more effectively blocks humoral responses that can lead to chronic injury and renal failure. During the Belatacept Evaluation of Nephroprotection and Efficacy as First-line Immunosuppression Trial (BENEFIT), the overall incidence and severity of acute rejection was higher in patients treated with belatacept compared to the CsA treatment group; however, renal function as measured by the calculated glomerular filtration rate (cGFR) was up to 10 cc/min higher in the belatacept treatment group, which suggests that long-term graft survival and renal function may be improved compared to CsA (Vincenti F. et al AJT 2012).

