# 2.2 Secondary Objective

- Assessing the incidence and severity of acute rejection 6 and 12 months post randomization
- Assessing the total cost associated with q-1M and q-2M dosing intervals
- Assessing the incidence of infection in the q-1M and q-2M patient groups
- Assessing the incidence of death and graft loss at 6 and 12 months
- Assessing the incidence of human leukocyte antigen (HLA) antibodies at randomization and at 6 and 12 months
- Assessing the frequency of clinic visits, hospitalizations, and transplant biopsies in the two patient groups

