# 6.3 Rejection

The occurrence of rejection requires special consideration:

- In the standard of care q-1M dosing group, any grade of rejection will be treated in accordance to our established ETC protocol for the treatment of rejection (Appendix 1).
- In the treatment arm, q-2M dosing group, any grade of rejection will be treated in accordance to our established ETC protocol for the treatment of rejection (Appendix 1).
   However, depending on the grade of rejection, study subjects will either remain in the q-2M treatment group or be converted over to the standard of care q 1M group.
  - If the rejection is graded as borderline or 1A: the patient will remain in the q-2M treatment arm with close follow up and surveillance consistent with routine practice.
  - If the rejection grade is 1B or greater, then the patient will be converted back to q-1M standard of care dosing but will remain in the study.
  - If the rejection is antibody mediated rejection (AMR), then the patient will be converted back to q-1M standard of care dosing but will remain in the study.

Rejection Grade	Gro	oup
	Q-1M	Q-2M
Borderline or 1A	Remain inQ-1M	Remain in Q-2M
1B or Greater	Remain in Q-1M	Convert to Q-1M
AMR	Remain in Q-1M	Convert to Q-1M

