# 9. Study Procedures and Assessments

# See Appendix 3.

# 10. Statistical Analysis

All analyses will be conducted on the intent-to-treat (ITT) population. The distribution of continuous outcome measures will be examined, and non-parametric equivalents of the two-sample t-test will be used to assess the statistical significance of non-normally distributed outcomes.

Statistical significance of the mean difference in eGFR between the q-4 and q-8 treatment groups at 12 months post-randomization will be assessed using the two-sample independent t-test statistic. The incidence of clinically suspected or biopsy-proven acute rejection (and date of acute rejection) will be collected based upon final ETC biopsy-proven acute rejection. We will describe acute rejection rates at 6 and 12 months post-randomization for the overall cohort and for the q-1M and q-2M treatment groups by calculating time to acute rejection. Kaplan-Meier analyses examining time to acute rejection will be used for comparisons by treatment group, with the log-rank test used to assess statistical significance. Potential differences in the severity of acute rejection between the treatment groups will be assessed by comparing the proportions of grade IIA and lower rejections and grade IIB and higher rejections between the treatment groups. Statistical significance of acute rejection severity will be assessed using the two-sample independent t-test statistic.

The incidence of infection in the q-4 and q-8 treatment groups will be collected based on labs performed at regular intervals throughout the study duration. Differences in the incidence of infection by treatment group will be assessed using the two-sample t-test statistic. The incidence of death and graft loss will also be determined, and the death rate and graft loss rates will be calculated at 6 and 12 months post-randomization. Kaplan-Meier analyses examining time to death and time to graft loss will be used for comparisons by treatment group, with the log-rank test used to assess statistical significance.

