# **ETC Rejection Protocol**

Borderline	Mini Pulse     No change in maintenance immunosuppression
ACR 1A	
 
Steroid Pulse
 
6 week prednisone taper
 
Rebiopsy in 1 month if SCr not improved
 

ACR 1B, 2A	
 
Thymoglobulin (7 days)
 
6 week prednisone taper
 
If on belatacept and Prograf, reduce Prograf goal trough to 3-5 ng/ml. Then taper per protocol.
 
For patients on belatacept and weaned from Prograf, no change in maintenance immunosuppression.
 

ACR 2B	
 
Thymoglobulin (10 days)
 
6 week prednisone taper
 
If on belatacept and Prograf, reduce Prograf goal trough to 3-5 ng/ml. Then taper per protocol.
 
For patients on belatacept and weaned from Prograf, no change in maintenance immunosuppression.
 

ACR 3	
 
Thymoglobulin (14 days)
 
6 week prednisone taper
 
If on belatacept and Prograf, reduce Prograf goal trough to 3-5 ng/ml. Then taper per protocol.
 
For patients on belatacept and weaned from Prograf, no change in maintenance immunosuppression.
 

AMR	Plasmapheresis/ IVIG

ACR – acute cellular rejection, AMR – antibody mediated rejection

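### The severity analysis has no class for antibody-mediated rejection and pools grades 1B and IIA with 1A, so an excess of these under q-2M dosing would not show as greater severity

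*Combined protocol and SAP*

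**What the plan says.** Section 2.2 lists as a secondary objective "Assessing the incidence and severity of acute rejection 6 and 12 months post randomization". Section 10 gives the only severity analysis: potential differences are assessed by "comparing the proportions of grade IIA and lower rejections and grade IIB and higher rejections between the treatment groups". The test follows: "Statistical significance of acute rejection severity will be assessed using the two-sample independent t-test statistic". Section 10 does not mention AMR here, does not say whether the proportions are of rejections or of randomized patients, and does not say whether borderline changes count as rejection.

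Elsewhere the protocol sorts rejections differently. Section 6.3 has three groups for patients on q-2M:
- Borderline or 1A: "If the rejection is graded as borderline or 1A: the patient will remain in the q-2M treatment arm".
- Cellular grade 1B and above: "If the rejection grade is 1B or greater, then the patient will be converted back to q-1M standard of care dosing".
- AMR: "If the rejection is antibody mediated rejection (AMR), then the patient will be converted back to q-1M standard of care dosing".

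The ETC Rejection Protocol has rows for borderline, ACR 1A, ACR 1B and 2A, ACR 2B, ACR 3 and, separately, AMR. Its footnote reads "ACR – acute cellular rejection, AMR – antibody mediated rejection". Borderline and 1A are treated with steroids, and thymoglobulin first appears in the row for 1B and 2A. The IIB line also has a place in the protocol: Sections 8.1 and 8.2 use it to exclude patients by rejection history.

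**The concern.** The two analysis classes do not cover the categories that the protocol itself uses. AMR has no grade on the IIA/IIB scale, so analysts could drop it, put it in either class or report it apart, and each could claim to follow the plan. Grades 1B and IIA do have a class, but it is the lower one, shared with 1A.

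The trial aims to show that the longer interval brings no loss of renal function and no increase in acute rejection. If q-2M dosing shifted rejections towards 1B, IIA or AMR, the severity comparison could read as no difference. A reader could then take the severity part of the objective as reassuring when the analysis had no means of detecting that shift.

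**Working it through.** **No stated figure to reproduce.** The documents give no rate, sample size or power for severity. The acute-rejection table in Section 10 concerns overall incidence. Its 2% versus 9% row (50 per group) follows from a non-inferiority formula with equal true rates, one-sided alpha 0.05 and 80% power: 2 × 0.02 × 0.98 × (1.645 + 0.842)² / 0.07² = 49.5, rounded up to 50. It is used below only as a source of rates.

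**Step 1: place each category in each scheme.**

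| Category | Section 6.3, q-2M patient | ETC Rejection Protocol | Section 10 severity class |
|---|---|---|---|
| Borderline | stays on q-2M | mini pulse | lower, if counted as rejection |
| 1A | stays on q-2M | steroid pulse | lower |
| 1B | converts to q-1M | thymoglobulin, 7 days | lower |
| IIA | converts to q-1M | thymoglobulin, 7 days | lower |
| IIB | converts to q-1M | thymoglobulin, 10 days | upper |
| III | converts to q-1M | thymoglobulin, 14 days | upper |
| AMR | converts to q-1M | plasmapheresis/IVIG | none |

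Of the five categories that trigger conversion, two are counted as severe, two are not, and one is unclassified.

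**Step 2: the unstated denominator.** If the proportion is taken among rejections, extra 1B or IIA events lower the IIB-or-higher share. With invented counts, one IIB among 4 rejections is 25%. Add four 1B or IIA events and it is 1 of 8, or 12.5%. The arm with more rejections then looks milder.

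**Step 3: how many events to expect.** Section 8 gives 83 per arm, and Section 10 expects a 1-2% rejection rate.
- Any grade, per arm: 83 × 0.01 = 0.83 to 83 × 0.02 = 1.66.
- Any grade at 9% in q-2M: 83 × 0.09 = 7.47.

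The documents give no grade distribution. Assume that IIB or higher makes up 5-20% of rejections and that 1B, IIA or AMR makes up 40-60%. At 2% versus 9%:
- IIB or higher, q-1M: 1.66 × 0.05 = 0.08 to 1.66 × 0.20 = 0.33 events.
- IIB or higher, q-2M: 7.47 × 0.05 = 0.37 to 7.47 × 0.20 = 1.49 events.
- Chance of no such event in either arm, with share s: (1 − 0.02s)^83 × (1 − 0.09s)^83. This is 0.633 at s = 0.05 and 0.159 at s = 0.20.
- Power of a two-sided 0.05 Fisher test on this class: at most 0.3%.
- 1B or greater, or AMR (combined share 45-80%): 1.66 × 0.45 = 0.75 to 1.66 × 0.80 = 1.33 events in q-1M, and 7.47 × 0.45 = 3.36 to 7.47 × 0.80 = 5.98 in q-2M. Fisher power is about 6-26%.

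**Step 4: a constructed example.** Suppose q-1M has two rejections, both 1A, and q-2M has seven: one 1A, five 1B or IIA, and one AMR.
- Planned cut per randomized patient: 0/83 versus 0/83 in the upper class, AMR unplaced, and the t-test undefined because there is no variance.
- 1B or greater, or AMR: 0/83 versus 6/83 (7.2%), Fisher p = 0.028. Among rejections only, 0/2 versus 6/7, p = 0.083.

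The example shows that a pattern can vanish under the planned cut. It does not show that a signal is likely, and the p-value is fragile: 5 versus 0 gives 0.059, and 6 versus 1 gives 0.117.

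**The case against.** **The IIB cut has a basis in the protocol.** It matches the eligibility boundary, and the ETC table lengthens thymoglobulin at 2B. This stands, and it is a reason to keep the split. But eligibility screens past history and does not define on-study severity, and it does not solve the AMR gap.

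**Section 6.3 is a dosing rule, not a severity scale.** Also true. A reader might infer that the protocol defines 1B or greater, or AMR, as severe; it never says so. What the documents support is narrower: they group these categories together for conversion, and the severity analysis separates them.

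**The 1A/1B call is exposed to bias.** It decides dosing in the q-2M arm only, and the documents describe no blinding of biopsy reading. A measure at that boundary is more open to arm-dependent grading than one at IIA/IIB. This stands as a drawback of the added measure.

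**The signal is partly visible elsewhere.** Section 10 compares time to rejection by log-rank test without a grade restriction, and compares donor-specific antibody at 6 and 12 months. Section 4.1 follows changes in immunosuppression, and the Section 4.4 thresholds count all biopsy-proven rejection in the q-2M group. In the constructed example, 7 versus 2 rejections would enter the incidence analysis, provided AMR counts as acute rejection. This limits the consequence, but none of these is a severity comparison.

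**Power is low under either cut.** Agreed, which favours a full table by category over reliance on a test.

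**The humoral argument.** A reader might infer from "belatacept more effectively blocks humoral responses that can lead to chronic injury and renal failure" that a longer interval should be expected to raise AMR. That statement is limited to animal models and compares belatacept with earlier agents. Both arms here receive belatacept, so it says nothing direct about the interval. The AMR gap stands without it.

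**Conclusion.** The point holds for 1B, IIA and AMR. As the plan is written, an excess of these under q-2M would not appear as greater severity, and if the denominator is rejections, extra 1B or IIA events could make q-2M look milder.

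Two stronger readings are tempting and not supported. One is that no rejection prompting conversion can show as severe: IIB and III are counted in the upper class. The other is that the trial would overlook an increase in rejection: incidence and donor-specific antibody are compared by arm regardless of this cut. The defect is confined to the severity part of one secondary objective and does not touch the primary eGFR comparison.

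That the upper class will be nearly empty rests on the planned 1-2% rate, which gives 0.83-1.66 rejections of any grade per arm. Under the assumed grade shares it usually holds none to about two events in all, even at 2% versus 9%. Those shares are assumptions, and eligibility alone does not establish the claim, because it concerns earlier rejections. The change is worth making because the plan leaves AMR unclassified and the repair costs little.

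**What to change.** Amend the severity paragraph in Section 10 as follows.
1. Use all randomized patients per arm as the denominator, and say so.
2. Tabulate each patient's worst rejection by arm: none, borderline, 1A, 1B, IIA, IIB, III, with AMR as its own class. Say how a patient with both cellular rejection and AMR is shown.
3. State whether borderline counts as rejection. Section 6.3 treats it as a grade, while Sections 8.1 and 8.2 count episodes from 1A upward.
4. Add the proportion per arm with 1B or greater, or AMR, with an exact confidence interval for the difference.
5. Keep the IIB-or-higher split alongside it, for continuity with the eligibility boundary.

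The cost is wording: grade and AMR status are already needed to apply Section 6.3. The drawbacks are one more low-event comparison, with about 6-26% power at 2% versus 9% under the assumed shares, and the exposure of the 1A/1B call to arm-dependent grading. The report should state both. No dosing or treatment rule changes.

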# 8. Study Population

The trial population consists of adults ≥18 years of age who are first-time transplant recipients of either living donor or deceased donor renal transplants. Patients of all races and ethnicities will be included.

This is an intention to treat, randomized, controlled trial. There will be a total of 166 subjects, randomized in equal numbers, 83 patients in each arm. We anticipate needing to consent/enroll 200 patients to achieve 166 randomized subjects accounting for an approximate 15% screen failure rate. All patients will be actively followed in the study for 12 months following enrollment. The study is projected to last 2 years.

Before any study procedures are performed, the details of the study will be described to subjects, and they will be given a written informed consent document to read. Patients who consent to participate in the study will sign and date the informed consent document in the presence of study personnel. Only patients who have given informed written consent will be included in this study.

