The mean eGFR at one year post-transplant for patients receiving belatacept at the Emory Transplant Center has been found to be 60.2 ml/min/1.73 m² with a standard deviation of 14.5 ml/min/1.73 m². When patients with an eGFR less than or equal to 35 ml/min/1.73 m² are excluded, the mean eGFR at one year post-transplant has been found to be 61.5 ml/min/1.73 m² with a standard deviation of 13.1 ml/min/1.73 m². Based on this inclusion criterion, the table below details several scenarios of potential sample size for different equivalence margins in order to attain 80% power for a significance level (alpha) of 0.05.

Calculated GFR is a continuous variable and will be assessed at monthly intervals (increasing to every two weeks from week 4 to 16 in the q-2M group) throughout the study. The secondary time points of rejection, death, graft lost, and HLA antibody production will be assessed at 6 and 12 months. Total cost, clinic visits, hospitalizations, biopsies and patient satisfaction will be assessed at 12 months.

Assuming a standard deviation of 13.1 ml/min/1.73 m^2:

Equivalence margin	N per group	Sample Size (total
(ml/min/1.73 m  )		N)
5.0	119	238
5.5	98	196
6.0	83	166
6.5	71	122
7.0	61	122

For example, assuming the standard deviation for eGFR at one year post-transplant is 13.1 ml/min/1.73 m^2, 166 patients total (83 per treatment group) are required to be 80% sure that a

two-sided 95% confidence interval will exclude a difference in mean eGFR between the treatment groups of more than 6.0 ml/min/1.73 m^2.

This study also aims to compare the secondary outcome of acute rejection rate between the q-1M and q-2M dosing interval groups. The one-year post-transplant acute rejection rate among patients treated with belatacept is expected to be 1-2%; based on this assumption, the table below details several scenarios of potential sample size for absolute differences in acute rejection rate in order to attain 80% power for a significance level of 0.05.

AR rate for reference group	AR rate for intervention group	Absolute difference	N per group	Sample Size
(q-4)	(q-8)	difference		(total N)
1%	4%	3%	137	274
1%	5%	4%	77	154
1%	6%	5%	49	98
1%	8%	7%	25	50
2%	5%	3%	270	540
2%	7%	5%	97	194
2%	8%	6%	68	136
2%	9%	7%	50	100

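### The t-test for rejection severity has no stated denominator and, at the plan's own 1-2% rejection rate, will often or usually have too few rejections to be computed

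*Combined protocol and SAP*

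**What the plan says.** Section 2.2 names incidence and severity of acute rejection at 6 and 12 months as the first secondary objective. For severity, section 10 plans "comparing the proportions of grade IIA and lower rejections and grade IIB and higher rejections between the treatment groups", and then: "Statistical significance of acute rejection severity will be assessed using the two-sample independent t-test statistic".

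The same section opens with "All analyses will be conducted on the intent-to-treat (ITT) population". It does not say whether the severity proportions are taken over rejections, over patients who reject, or over all randomised patients. It gives no rule for an arm with no rejections or very few. The non-parametric fallback in section 10 is for continuous outcomes.

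On numbers, section 8 states: "There will be a total of 166 subjects, randomized in equal numbers, 83 patients in each arm". Section 10 states: "The one-year post-transplant acute rejection rate among patients treated with belatacept is expected to be 1-2" per cent.

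**The concern.** The two grade categories together make up all rejections and contain no level for a patient without rejection. The natural denominator is therefore the rejectors. That raises two problems.

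- **Too few data.** One or two rejectors per arm will often not support a t statistic at all.
- **Not a randomised comparison.** Rejection happens after randomisation and may depend on the dosing interval. If q-2M adds mild rejections, its share of severe ones falls, and the longer interval looks better on severity because it caused more rejection.

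This is the only planned comparison of severity, since the Kaplan-Meier and log-rank analysis addresses time to rejection and not its grade. At stake is half of one secondary objective.

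**Working it through.** **Inputs.** 83 per arm (section 8); rejection rate p = 1-2% (section 10). The documents give no share of rejections graded IIB or higher. I call it q, assume 5-25%, and also show 50%, the value most favourable to the test.

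**The plan's figures.** The 83 per group reproduces as an equivalence calculation with margin 6.0, SD 13.1, true difference zero, 80% power and each one-sided test at 0.05. The rejection sample-size table reproduces in all eight rows as a non-inferiority calculation with *both* arms at the reference rate and one-sided alpha 0.05. For the 1% versus 4% row, (1.645 + 0.842)² × 2 × 0.01 × 0.99 / 0.03² ≈ 136.0, rounded up to 137. Equal rates of 1-2% in both arms are therefore the plan's own working case.

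**Expected rejectors per arm.** 83 × 0.01 = 0.83; 83 × 0.02 = 1.66.

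**When the pooled t-test fails among rejectors.**

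1. An arm has no rejector: 1 − (1 − (1−p)^83)².
   - At 1%: 0.99^83 = 0.434, and 1 − 0.566² = 0.680.
   - At 2%: 0.98^83 = 0.187, and 1 − 0.813² = 0.339.
2. Add one rejector in each arm (zero degrees of freedom): add [83p(1−p)^82]².
   - At 1%: 0.680 + 0.364² = 0.812.
   - At 2%: 0.339 + 0.317² = 0.439.
3. Add zero pooled variance, where all rejectors within each arm fall in the same category. With b(k) the Binomial(83, p) probability and h(k) = q^k + (1−q)^k, the test is computable with probability Σ b(i) b(j) [1 − h(i)h(j)], summed over i, j ≥ 1 with i + j ≥ 3.

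| Not computable (rejectors only) | 1% both arms | 2% both arms |
|---|---|---|
| Empty arm | 68% | 34% |
| + one versus one | 81% | 44% |
| + zero variance, q = 5% | 98% | 90% |
| + zero variance, q = 25% | 91% | 67% |
| + zero variance, q = 50% | 88% | 58% |

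A Welch test needs at least two rejectors per arm and fails in at least 96% and 75% of trials.

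**Higher q-2M rates from the rejection table (q = 5-25%).** The pooled test is not computable in 67-90% of trials at 1% versus 4%, 53-82% at 1% versus 8%, 41-80% at 2% versus 5%, and 28-70% at 2% versus 9%.

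**Direction of the bias.** If an arm has r rejections, s of them severe, its share is s/r. With k extra mild rejections the share is s/(r + k), which is smaller although no severe rejection was avoided. Over all randomised patients the proportion stays s/83.

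**Alternative denominator: all 83 per arm.** The t-test is then undefined only if neither arm has a IIB-or-higher event, with probability (1 − pq)^166:

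- At 1%: 0.920 for q = 5%, 0.660 for q = 25%.
- At 2%: 0.847 for q = 5%, 0.435 for q = 25%.

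**What an exact test could show.** With 83 per arm, Fisher's two-sided p is 0.059 for 5 versus 0 severe events and 0.028 for 6 versus 0.

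**The case against.** **The denominator is inferred.** A reader might conclude that the plan restricts the comparison to rejectors. It does not say so, and it declares an intent-to-treat population. This stands. The intent-to-treat sentence does not settle the question either, since rejectors within that population are still a selected group. The conditioning problem therefore holds only on the rejectors-only reading.

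**Usually uncomputable is too strong as a general statement.** At 2%, the documents' own figures give 34% from empty arms and 44% with the one-versus-one case. Only zero-variance outcomes carry it past half. They do so for any value of q, but the size depends on an assumed share. In such trials the descriptive result, for example no severe rejection in either arm, can still be reported. At unequal rates the statement can fail: at 2% versus 9% with q = 25%, the test is computable in about 73% of trials (1 − 0.275). All of this stands. What remains is that equal rates of 1-2% are the planning case, and that more rejections make the test computable without removing the conditioning.

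**The 1-2% is a post-transplant rate.** It describes the first year after transplant, while patients enter at least a year after transplant. The plan applies it to this trial, so it is the right figure for checking the plan, but it does not predict the counts closely.

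**An exact test is hardly more informative.** Correct. The case for change is that the estimate can always be reported and compares the randomised groups. It is not a gain in power.

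**Conclusion.** The point holds in a limited form. The severity analysis lacks a denominator, and a t-test is unsuited to so few events. At 1-2% in both arms, on the rejectors-only reading, it cannot be computed in 91-98% (1%) or 67-90% (2%) of trials. These ranges rest on an assumed IIB-or-higher share of 5-25% and on counting zero-variance outcomes. Without any assumed share the figures are 81% and 44%. With all randomised patients as denominator they are 66-92% and 44-85%, under the same assumed shares.

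If rejection is more frequent under q-2M, the computational problem eases. The rejectors-only comparison can then favour the arm with more mild rejection.

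A reader might infer that the rejection analysis as a whole, or the trial's main conclusion, is compromised. The documents do not support that: the log-rank test of time to rejection and the primary eGFR comparison do not use this split. The change should be made, but it concerns one part of one secondary objective.

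**What to change.** In section 10, replace the severity t-test with a comparison over all randomised patients:

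- Report the number and proportion in each arm by worst rejection grade per patient, out of 83, at 6 and 12 months.
- Show antibody-mediated rejection as its own category. Section 6.3 and the ETC Rejection Protocol list it apart from the cellular grades, and the IIA/IIB split does not place it. The documents give no basis for ranking it with any cellular grade, so an ordinal score that does so should not be introduced without justification.
- Give the risk difference for IIB or higher with an exact interval, and Fisher's test if a p-value is wanted.
- Label the analysis descriptive.

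The cost is a few sentences, with no new data, visits or patients. The drawback is very low power: 6 versus 0 severe events are needed for p < 0.05. A non-significant result would support no claim that severity is the same under the two intervals, and the text should say so.

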# 2. Study Objectives

# 2.1 Primary Objective

The primary objective of this non-inferiority trial involving immunologically low-risk patients is to show that the GFR 12 months post-randomization is the same for patients who receive belatacept at q-4 and q-8 dosing intervals.

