The incidence of HLA donor specific antibodies (DSA) (e.g. presence or absence of HLA DSA) at 6 and 12 months post-randomization will be compared by treatment group, with statistical significance assessed using the two-sample independent t-test statistic. The frequency of clinic visits, hospitalizations, and transplant biopsies will be calculated for each patient and descriptive statistics (e.g. mean and standard deviation) reported by treatment group. Differences in the frequency of these outcomes at 12 months post-randomization will be compared by treatment groups using the two-sample t-test statistic.

The total cost associated with the q-1M and q-2M dosing intervals will be compared between the two treatment groups by calculating the mean total cost of infusions received by each subject. The time and cost associated with roundtrip travel to the ETC will be estimated using the distance between the residential addresses of subjects and the ETC. Statistically significant differences in the preceding secondary endpoints will be assessed using the two-sample

independent t-test statistic. Potential differences in patient compliance will be assessed using the two-sample independent t-test statistic to compare the proportions of missed infusion appointments between the q-1M and q-2M dosing treatment groups.

Equivalence testing is used to assess whether "practical equivalence" of the outcome of interest has been achieved between two groups. This study will compare the primary outcome of mean eGFR between the standard q-1M control group and the q-2M treatment group, with the hypothesis that mean eGFR will not vary between the groups by more than a pre-specified acceptable difference, or equivalence margin. In the context of equivalence testing, statistical power represents the probability of detecting a difference at least as large as the equivalence margin.

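### The 80% power at 83 per arm rests on a baseline-type SD and no loss after randomisation, and the calculation behind it has no reserve

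*Combined protocol and SAP*

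**What the plan says.** Section 10 reports eGFR one year after transplant at the centre as mean 60.2, SD 14.5. Without patients at or below 35 the figures become 61.5 and 13.1. The smaller SD is carried into the sample-size table: "Based on this inclusion criterion, the table below details several scenarios of potential sample size for different equivalence margins". The table's stated target is 80% power at alpha 0.05. At a margin of 6.0 it lists 83 per group, and the criterion that the text attaches to this number is: "two-sided 95% confidence interval will exclude a difference in mean eGFR between the treatment groups of more than 6.0".

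Section 8 then fixes the randomised number at the calculated number: "There will be a total of 166 subjects, randomized in equal numbers, 83 patients in each arm". The step from 200 consented to 166 randomised is attributed to screen failure.

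The framework is described in two ways. Section 2.1 has "The primary objective of this non-inferiority trial involving immunologically low-risk patients", while Section 10 sizes the trial on the hypothesis that "mean eGFR will not vary between the groups by more than a pre-specified acceptable difference, or equivalence margin". The primary comparison in Section 10 is an unadjusted two-sample t-test at 12 months after randomisation. Section 8.2 excludes GFR below 35, and Section 8.1 requires at least one year since transplant.

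**The concern.** The 13.1 is the spread of a variable cut on its own value. In the trial the cut acts on entry eGFR, but the analysed variable is eGFR a year later. Nothing keeps that value above 35, and Section 6.2 lists worsening kidney function and graft loss among the events to record. So 13.1 is a baseline-type SD applied to a later outcome, and unless entry and month-12 values are perfectly correlated, part of the removed spread returns.

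Separately, 83 is both the number needed for analysis and the number randomised. The protocol foresees withdrawal for pregnancy or plans for it (Section 6.1), premature withdrawal for adverse events (Section 4.1), and death and graft loss (Sections 2.2 and 10). The text available gives no loss rate and no method for a missing month-12 eGFR, and naming an intention-to-treat population does not supply the missing values.

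At stake is an interval too wide to settle whether the two-month schedule preserves renal function.

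**Working it through.** **Inputs.** From Section 10: margin 6.0, SD 13.1 (14.5 before exclusion), alpha 0.05, power 80%. From Section 8: 83 per arm. Assumptions, because the documents are silent: true difference 0, unselected month-12 SD 14.5, correlation r between entry and month-12 eGFR of 0.5 to 0.9, and loss of 5–10%.

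**1. Reproducing 83.** For equivalence by two one-sided tests at level a per side, n = 2[SD(z(1−a) + z(0.90))/margin]².

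- a = 0.05: 2[13.1 × (1.645 + 1.282)/6]² = 81.7, so 82. The t-based version gives 83, and it returns every N per group in the table (119, 98, 83, 71, 61).
- a = 0.025, a true two-sided 95% interval inside ±6.0: 101.
- Non-inferiority, one-sided 0.025: 75 (t-based 76).

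The table was therefore built on a 90% interval, not the 95% interval in the text.

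**2. Reserve.** t-based power at 83 is 80.4%, and 82 evaluable per arm falls below 80%. The largest SD that keeps 80% at 83 is 6/[(1.645 + 1.282) × √(2/83)] = 13.2.

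**3. Where 13.1 comes from.** Truncating Normal(60.2, 14.5) at 35 gives mean 61.5 and SD 13.2, close to the stated 61.5 and 13.1. The variance falls by 1 − 174.9/210.25 = 0.168.

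**4. Month-12 SD when selection acts at entry.** SD = 14.5 × √(1 − 0.168r²). At r = 0.5 this is 14.2; at r = 0.9 it is 13.5.

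**5. Power (normal approximation).** With k = 6/(SD × √(2/n)), equivalence power is 2Φ(k − 1.645) − 1 and non-inferiority power is Φ(k − 1.960). For example, at SD 13.5 and n = 83, k = 2.86, giving 78% and 82%. Loss of 5% leaves 79 per arm and 10% leaves 75.

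| Month-12 SD | n per arm | Equivalence, 0.05 per side | Non-inferiority, one-sided 0.025 |
|---|---|---|---|
| 13.1 | 83 | 81% | 84% |
| 13.5 (r = 0.9) | 83 | 78% | 82% |
| 14.2 (r = 0.5) | 83 | 72% | 78% |
| 14.5 | 83 | 69% | 76% |
| 13.1 | 79 | 78% | 82% |
| 13.1 | 75 | 75% | 80% |
| 13.5 (r = 0.9) | 75 | 72% | 78% |
| 14.2 (r = 0.5) | 75 | 66% | 74% |

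On the literal criterion (1.960 in place of 1.645 in the equivalence formula), power at SD 13.1 and n = 83 is about 68%.

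**6. Baseline adjustment.** Residual SD = 14.5 × √(1 − r²), which is 12.6 at r = 0.5 and 10.4 at r = 0.7. Equivalence power at 0.05 per side is 84.8% and 96% with 83 per arm, and 80% and 94% with 75. At r = 0.4 the residual SD is 13.3 and 85 per arm would be needed, so the gain depends on a correlation above roughly 0.4.

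**The case against.** A reader might infer that 83 per arm cannot deliver 80%, or that 80% is a ceiling reached only with perfect correlation and complete data. The documents do not support either statement. Section 2.1 declares non-inferiority. If that is judged at one-sided 2.5%, 83 per arm gives 84% at SD 13.1 and keeps 80% up to an SD of about 13.8, or with 75 evaluable per arm at SD 13.1. On the literal 95% equivalence criterion, by contrast, 80% is not reached even under the plan's own inputs. At a fixed SD the unsettled framework moves power from about 68% to 84%, more than the SD question does.

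Nor do the documents show that the month-12 SD must lie between 13.1 and 14.5. The other entry criteria (on donor-specific antibody, rejection history, proteinuria and creatinine rise) could narrow the spread, and decline or graft loss could widen it. No month-12 SD, correlation or loss rate is given. Loss may also be modest: patients with rejection stay in the study even when their dosing interval changes (Section 6.3), and chemistry is at least monthly (Section 7). Section 10 shows both SDs openly and words its conclusion conditionally, and the t-test is valid under randomisation.

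All of this stands. What it does not remove is that the calculation that produced 83 has no reserve, that the SD is not one for the analysed variable, and that no allowance is made after randomisation.

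**Conclusion.** The concern holds as one of unsupported power, not of demonstrated failure. On the equivalence calculation behind the table, power is 72–78% instead of 80% with no loss, and 66–72% with 10% loss. On a one-sided 2.5% non-inferiority reading a modest departure in SD or in loss costs little: power is 78–82% at the wider SDs, and reaches 74–78% only when wider SD and 10% loss combine. These ranges rest on an assumed unselected month-12 SD of 14.5, correlations of 0.5 to 0.9, an assumed loss rate and a true difference of zero. Because the plan does not settle which criterion its 80% refers to, it cannot be said which range applies.

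**What to change.** No additional enrolment is needed.

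1. State whether the primary conclusion is non-inferiority or equivalence, with the alpha per side and the matching confidence interval, and say which of these the 80% refers to.
2. Restate power at 83 per arm for month-12 SDs of about 13.5 to 14.5 and for 5–10% loss after randomisation, labelled as assumptions.
3. Make the primary comparison an ANCOVA on month-12 eGFR adjusted for M0 eGFR, or a repeated-measures model on the monthly values with the same adjustment. The schedule of events already has a basic chemistry panel at M0 and monthly in both arms. At a correlation of 0.5 this brings equivalence power (0.05 per side) to about 85% with no loss and just 80% with 10% loss; at 0.7 there is ample reserve. It would not rescue the literal 95% equivalence criterion at a correlation of 0.5, where power is about 74% with no loss.

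The cost is SAP wording. The downside is that the stated unadjusted power becomes slightly less favourable.
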